3. STATISTICAL METHODS

3.1 DEFINITION OF THE ANALYSED DATA SETS

According to the proposed analysis, several analysis sets have been defined as follows:

3.1.1 Efficacy sets

3.1.1.1 Intent-To-Treat Set (ITT)

This set is defined as all randomized patients considered as randomised (i.e. regardless of allocation errors) patients and having received at least one dose of the IMP.

3.1.1.2 Per Protocol Set (PP)

It includes all ITT patients without any major protocol deviation. These major deviations will be reviewed by the data review committee and listed in the final version SAP prior to final database lock.

3.1.2 Safety set (SS)

This set is defined as all patients receiving at least one dose of IMP and considered ‘as treated’ (i.e. assigned to the ‘as treated’ group regardless of randomization errors). If all randomized patients received their allocated treatment and if there is no

randomization error, the 'as treated' analysis will be the same 'as randomized' analysis and Safety set will be the same than Intent-to-treat set.

3.2 DATA REVIEW COMMITTEE

The members of the data review committee are the study coordinator, members of the scientific committee, representatives of the sponsor, members of the CRO (project manager, data manager, statistician, medical writer).

The data will be reviewed during a meeting in a blinded manner.

The data review committee will define :

- 1) the deviations to the protocol as minor and major, thus enabling the specific definition of each of the populations.
- 2) Missing data for the primary endpoint: missing data will be confirmed by the scientific committee.

Final decisions will be taken by the scientific committee only.

3.3 STATISTICAL ANALYSES

3.3.1 Generalities

The analysis is carried out on a PC provided with Windows Seven operating system.

The analysis is performed with the software SAS® version 9.4.

The inferential analyses are preceded by descriptive analyses.

The quantitative variables are described by number of data available and missing, mean, standard deviation, the 1st and the 3rd quartile, median, minimum and maximum.

The qualitative variables are described by number of data available and missing, frequency and percentage per modality. The category missing are displayed only if there are actually missing values. Percentages are calculated on the total of non-missing recorded categories.

3.3.2 Interim analyses and Multiplicity issue

No interim analysis is planned.

No multiplicity adjustment is necessary for the primary analysis as there is only one primary criterion and two arms compared. The 2-sided nominal alpha level of

significance is set to 5%. Results for the two components of the composite primary endpoint will be individually examined without statistical hypothesis testing.

Secondary efficacy parameters will be tested for superiority at the 5% level of the Clottafact[®] arm, compared to the placebo arm. Secondary efficacy variables will be examined and may contribute to supportive information to the effectiveness. We distinguish two types of secondary endpoints: (1) Key secondary endpoints are defined as highly clinically relevant endpoints (ie. based on clinical practices). Statistical methods for addressing multiplicity issues will be used to test sequentially key secondary endpoints (ie. Hochberg procedure); (2) other secondary endpoints will be analysed in an exploratory purpose.

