3.3.6.2 Primary analysis of the primary endpoint

3.3.6.2.1 Hypothesis

- Null hypothesis:

H0: the true failure rate in the Clotfact[®] randomised group = the true failure rate in the placebo group.

- Alternative hypothesis:

H1: the true failure rate in the Clotfact[®] randomised group \neq the true failure rate in the placebo group.

The nominal two-sided level of significance is set to 5%.

The primary analysis will be conducted primarily in the ITT set.

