Baseline covariates will be tested separately in univariate logistic regression models which will be the primary model to estimate the treatment effect by covariate level with its 95%CI (see §7.4 for SAS code). Forest plots displaying treatment effects (odds ratios) along with their 95%CIs will be displayed across covariates levels.

A multivariate analysis will be done to test in the model the following relevant covariates and interactions. Center, the total blood lost, the tranexamic acid intake, lost of haemoglobin compared to the reference level, heart rate and their interactions will be analysed in a stepwise logistic regression model.

3.3.6.3 *Secondary efficacy variables*

Analyses of secondary efficacy endpoints will be primarily conducted in the ITT set. Sensitivity analyses will be performed in the PP set.

3.3.6.3.1 *Description of secondary efficacy variables*

Secondary efficacy variables are detailed in §1.10.2. We distinguish two types of secondary endpoints:

- **Key secondary efficacy variables :**
 - 1- Calculated and adjustment of total blood loss 48 hours following IMP administration

The calculation and adjustment of total blood loss with regards to transfusional needs will be calculated as follows:

Total blood loss (mL) = blood loss calculated + blood loss compensated by transfusion

With:

-Calculated blood loss = Pregnancy total blood volume x (Ht0 – Htf) x (100/35)

- Pregnancy total blood volume = (Maternal weight measured before pregnancy x 65 mL/kg) x 1.4
- Ht0: last available value of haematocrit before delivery
- Htf: value of haematocrit in the morning of D2

-Blood loss compensated by transfusion (mL) = n RBC x 500mL (with n corresponding to the number of transfused units and 500mL = total transfused blood volume of 300 mL RBC with Ht of 60%).

2- Percentage of patients requiring any need for rescue procedure

The percentage of patients requiring any need for rescue procedure is defined as follows:

- at least one of the following invasive procedure within 48 hours following IMP administration :
 - pelvic arteries embolization,
 - surgical vascular ligation,
 - uterine ligation (B Lynch or other techniques),
 - hysterectomy
 - intrauterine balloon
- and/or administration of recombinant active Factor VII (rFVIIa),
- and/or fibrinogen rescue.

3- Percentage of patients requiring the use of intrauterine balloon within 48 hours following IMP administration.

- **Other secondary efficacy variables :**

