- 1- Change in plasma fibrinogen level (g/L) between H2 and H0
- 2- Change in plasma fibrinogen level (g/L) between H6 and H0
- 3- Change in plasma fibrinogen level (g/L) between D2 and H0
- 4- The same changes will be calculated for Hb, Ht and RBCs
- 5- Duration of haemorrhage (hours): end time of haemorrhage – start time of haemorrhage

- 6- Duration in the obstetrics room (from arrival hour in obstetrics room to delivery hour)
- 7- Duration of hospitalization (from arrival date in obstetrics room to hospital discharge date)
- 8- Number of days in resuscitation and/or intensive care and/or PICU and/or continuous care units (admission date and discharge date)
- 9- Number of days with assisted ventilation

3.3.6.3.2 *Analyses of secondary efficacy variables*

3.3.6.3.2.1 Analyses of key secondary variables

The analyses of key secondary variables will be tested with the Hochberg step-up method:

- 1- Calculated/estimated volume of total blood loss, 48 hours following IMP administration

The estimated/calculated volume of total blood loss 48 hour after IMP administration will be compared between the Clottafact[®] group and placebo group by a t test or non parametric test.

- 2- Percentage of patients requiring any need for rescue procedure

The percentage of patients requiring any need for rescue procedure within 48 hours following IMP administration will be calculated and chi-square or Fisher exact tests will be used to compare between the Clottafact[®] group and placebo group.

- 3- Percentage of patients requiring the use of intrauterine balloon within 48 hours following IMP administration

The percentage of patients requiring the use of intrauterine balloon within 48 hours following the administration will be calculated and chi-square or Fisher exact tests will be used to compare between the Clottafact[®] group and placebo group.

3.3.6.3.2.2 Other analyses of secondary variables

Other secondary endpoints will be analysed in an exploratory purpose.

3.3.6.3.2.2.1 Analyses of the change from baseline in plasma fibrinogen level, Hb and Ht

The evolution in plasma fibrinogen level, Hb and Ht will be analysed at H2, H6 and D2 following IMP administration with a Mixed Model of Repeated Measurements comparing the Clottafact[®] group and placebo group.

3.3.6.3.2.2.2 Analyses of the evolution of haemorrhage

3.3.6.3.2.2.2.1 Analyses of haemoglobin level

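### The SAP sets no condition linking the Hochberg family of key secondaries to the primary, so error over the combined set can exceed 5% (about 7% to 9%, at most about 10%)

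*SAP*

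**What the plan says.** **Primary.** SAP 3.3.6.2.1 states one hypothesis pair and adds: "The nominal two-sided level of significance is set to 5" per cent. SAP 3.3.2 gives the reason for leaving it unadjusted: "No multiplicity adjustment is necessary for the primary analysis as there is only one primary criterion and two arms compared".

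**Secondaries in general.** SAP 3.3.2 continues: "Secondary efficacy parameters will be tested for superiority at the 5% level of the Clottafact" arm against placebo. It describes secondary results as information that may support effectiveness. It then separates key secondaries, chosen for clinical relevance, from the rest, which are exploratory.

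**Key secondaries.** SAP 3.3.2 says: "Statistical methods for addressing multiplicity issues will be used to test sequentially key secondary endpoints (ie. Hochberg procedure"). SAP 3.3.6.3.2.1 says: "The analyses of key secondary variables will be tested with the Hochberg step-up method". SAP 3.3.6.3.1 lists the members of the family:

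1. "Calculated and adjustment of total blood loss 48 hours following IMP administration"
2. "Percentage of patients requiring any need for rescue procedure"
3. "Percentage of patients requiring the use of intrauterine balloon within 48 hours following IMP administration"

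**Link between the two.** There is none. The multiplicity row of the change table in SAP 2.2 repeats the text of 3.3.2 and records that the protocol had no rule. Protocol 12.10.1.2.5, whose heading covers multiple comparisons, says only that no interim analysis is planned.

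**The concern.** Picking out three secondaries for formal multiplicity control gives a significant result on one of them more weight than an exploratory finding. The SAP does not say whether that weight survives a failed primary. An analyst who follows the text would run the primary at 5% and the Hochberg family at another 5%, and could report a multiplicity-controlled key-secondary finding after a null primary. Another analyst might take the word for sequential testing in 3.3.2 to mean that the primary comes first. It does not establish that: Hochberg works step-up on the ordered p-values inside the family and takes no account of a test outside it.

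At stake is what may be concluded in one situation, where the primary fails and a key secondary has a small p-value. The two readings then give different conclusions from the same data, and under the permissive one the overall false-claim rate is above 5%.

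**Working it through.** **The plan's own figure.** The documents state no error rate for the primary and key secondaries combined. The design figure for the primary does reproduce. Protocol 12.3 gives 42% against 27%, two-sided 5%, 90% power, and a Z test with unpooled variance:

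n = (1.960 + 1.282)² × (0.42 × 0.58 + 0.27 × 0.73) / 0.15² = 205.8, so 206 per group.

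Then 412 / 0.95 = 433.7, so 434. Nothing below affects these numbers.

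**Inputs for the error rate.** The primary is at two-sided 0.05 (SAP 3.3.6.2.1). There are three key secondaries (SAP 3.3.6.3.1), tested by Hochberg at 0.05, which compares the ordered p-values with 0.05, 0.025 and 0.0167 from largest to smallest. The documents give no correlations between the test statistics, so a range is assumed.

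**Identity used.** P(any false claim) = P(primary rejects) + P(family rejects and primary does not).

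**Bounds under the global null.**

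- Sum of the two levels: 0.05 + 0.05 = 10.0%.
- Two independent 5% tests: 1 − 0.95 × 0.95 = 9.75%.
- Hochberg on three independent endpoints rejects in 4.92% of simulated null trials, not the full 5%, so all four independent gives 1 − 0.95 × (1 − 0.0492) = 9.67%.

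**Simulation.** Four jointly normal null statistics, 2,000,000 draws per row. The Monte Carlo standard error of a 9% rate is √(0.09 × 0.91 / 2,000,000) = 0.02 percentage points. Correlations are listed in the order blood loss, rescue, balloon. Among the key secondaries the order is blood loss–rescue, blood loss–balloon, rescue–balloon.

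| Primary with key secondaries | Among key secondaries | Hochberg family alone | Any false claim, no condition | Family rejects, primary does not | Any false claim favouring active |
|---|---|---|---|---|---|
| 0, 0, 0 | 0, 0, 0 | 4.92% | 9.68% | 4.68% | 4.94% |
| 0, 0, 0 | 0.3, 0.3, 0.8 | 4.38% | 9.15% | 4.16% | 4.64% |
| 0.3, 0.3, 0.3 | 0.3, 0.3, 0.8 | 4.38% | 8.91% | 3.89% | 4.46% |
| 0.5, 0.5, 0.5 | 0.5, 0.5, 0.8 | 4.26% | 8.33% | 3.30% | 4.18% |
| 0.7, 0.4, 0.4 | 0.4, 0.4, 0.8 | 4.30% | 8.16% | 3.17% | 4.08% |
| 0.8, 0.5, 0.5 | 0.5, 0.5, 0.9 | 4.05% | 7.57% | 2.58% | 3.80% |
| 0.8, 0.7, 0.7 | 0.7, 0.7, 0.9 | 3.83% | 7.07% | 2.04% | 3.54% |

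A separate run of 400,000 null trials with one common correlation for all four statistics gives 9.7%, 9.3%, 8.5% and 7.4% at correlations 0, 0.3, 0.5 and 0.7.

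**Which rows are plausible.** The endpoints overlap by construction. The balloon is key secondary 3 and also a component of key secondary 2 (SAP 3.3.6.3.1). RBC units count towards the primary (SAP 3.3.6.1.1) and enter calculated blood loss at 500 mL per unit. The primary uses the fall in Hb and blood loss uses the fall in Ht. Independence is therefore the extreme case, and the correlated rows, about 7% to 9%, are the realistic ones.

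**With a condition on the primary.** Under the global null a key-secondary claim then requires a primary rejection, so P(any false claim) = P(primary rejects) = 5% (simulated 4.99% to 5.03%).

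**The case against.** The strongest reply is that nothing formal is broken. The primary keeps its 5% error, and Hochberg holds the key secondaries at or below 5% under independence or positive dependence. The SAP calls secondary results supportive, never applies the word confirmatory to them, and nowhere promises control across the two families. For a phase IV trial with one primary criterion, control within the family is a defensible choice.

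Most of that stands, and it rules out four stronger readings that a reader might infer:

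- *That the SAP orders the family to be tested whether or not the primary succeeds.* It does not say so. It is silent, and the silence permits such testing.
- *That the error rate nearly doubles.* That is the independence figure of 9.7%, and the overlap between the endpoints argues against independence.
- *That a false confirmatory claim is planned.* The text speaks of support only.
- *That multiplicity control reaches only part of the formal tests.* All four are controlled within their own family. What is missing is control across the families.

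The word for sequential testing is also a side issue: SAP 3.3.6.3.2.1 names the step-up method correctly, and removing the word would change no result.

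The reply does not settle what may be said after a failed primary. The supportive label covers all secondaries, yet the SAP then sets three apart from the exploratory ones and controls their error. That control has little purpose unless a significant result carries inferential weight, so the SAP should state when it does.

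**Conclusion.** The point holds as a gap in the testing rules. As written, a 5% Hochberg family stands beside a 5% primary with no condition between them, and a multiplicity-controlled key-secondary claim can follow a failed primary.

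Under the global null, the chance of at least one false claim is about 7% to 9% with positive correlation and at most about 10%. Across all the rows computed, including independence, that is about 1.4 to 1.9 times 5% (7.1 / 5 to 9.7 / 5). Counting only claims in favour of the active arm, it is 3.5% to 4.9% against 2.5%. These figures rest on assumed correlations, on jointly normal test statistics, and on a key-secondary rejection being presented as a formal finding despite a null primary. If no such claim would ever be made, the inflation has no practical effect, but the SAP does not say that. The validity of the primary test is not in question.

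**What to change.** State in SAP 3.3.2 and again in 3.3.6.3.2.1 that the Hochberg procedure on the three key secondaries is applied at two-sided 5% only if the primary analysis is significant at two-sided 5%. State also that otherwise their p-values are descriptive and support no formal claim.

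This returns the overall rate to 5% under the global null. If the primary effect is real, Hochberg still limits false key-secondary claims to 5%. A lighter alternative is to declare that the key secondaries support no formal claim in any case. That also removes the ambiguity, but it gives up formal key-secondary claims even after a positive primary.

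The cost is one sentence in each of two sections, and the loss of any formal key-secondary claim if the primary fails. Sample size, the primary model and the Hochberg calculation itself are unchanged.

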3.3.3 Handling of Missing Data

As a general rule, missing data will not be replaced.

Missing data for the primary endpoint occurs when the primary endpoint cannot be evaluated. Missing data will be confirmed by the scientific committee during the data review meeting (see 3.2). When the Hb level within the 48 hours following IMP administration is missing, the Hb value in the 48 hours following inclusion that not be collected as part of the study will be used to calculate the lose of Hb compared to the reference Hb level and for the primary endpoint evaluation.

No imputation of missing data will be proposed for the primary analysis of primary endpoint. The primary analysis will thus be performed on the Full analysis set (FAS), which will be as close as possible to the randomized set.

Sensitivity analyses of the primary endpoint will be proposed as follows:

- Primary sensitivity analysis (MAR assumption): a multiple imputation approach (MI) will be used assuming a missing at random (MAR) mechanism will be used to handle missing data. A multiple imputation approach by Fully Conditional Specification (FCS) will be used to handle missing data of the primary efficacy endpoint.

- Secondary sensitivity analysis (MNAR assumption): all missing data for the primary endpoint will be estimated as failures assuming a missing not at random mechanism.

When needed, to be able to calculate durations, incomplete dates will be estimated according rules specified in the section 6.1.1. and will be reviewed by the scientific committee.

All estimated or replaced data will be edited along with a flag in the statistical appendices.

3.3.4 Study Patients

3.3.4.1 Patient Disposition

The number of patients who were enrolled and having been treated at least once by the IMP as well as those who fulfilled the inclusion and exclusion criteria will be summarised overall.

The number of patients in each center will be displayed overall and by group by means of contingency table in the ITT Set.

3.3.4.2 Protocol deviations

The number and percentage of patients with any protocol deviation, which is listed by deviation category, will be tabulated overall and by study treatment group in the ITT Set.

3.3.4.3 Analysis set

The number and percentage of patients in each analysis set will be displayed overall and by group in the ITT Set. The number and percentage of patients with definitive discontinuation and their reasons will be tabulated overall and by group in the ITT Set.

3.3.5 Demographics and Other Baseline Characteristics

Demographic and baseline characteristics of patients will be analysed on the ITT and PP set. Data will be presented per randomisation group. Statistical tests will not be performed to compare randomisation groups at baseline. Possible differences between groups at baseline will be judged from a clinical point of view only.

3.3.5.1 Demographic Characteristics, Medical History and Diagnoses

All demographic characteristics and all medical history data will be presented per randomisation group. Medical and surgical history data recorded at inclusion visit will be coded using the MedDRA dictionary version 17.1. All data will be summarised by Primary System Organ Class (SOC) and Preferred Term (PT) according to treatment group.

Pregnancy and data related to the delivery up to randomisation will also be presented in this section.

3.3.5.2 Previous Treatments

All previous treatments will be listed by patient with the associated Anatomical Therapeutic Chemical (ATC) codes for the WHO drug dictionary March 1, 2014 version.

Descriptive statistics will be produced to describe the previous treatments by anatomical therapeutic (ATC) name and preferred name according to treatment group.

Intravenous fluids and tranexamic acid before study treatment administration will be described according to treatment group.

Volume administered (mL), dose (g), duration of treatment administration and duration since start of delivery will be also presented.

3.3.5.3 Baseline Efficacy Variables

All efficacy variables will be presented by randomisation group. Baseline data are defined as the last available data before the start of IMP infusion.

Date and time of the last available Hb (g/dL) determination will be presented. The month of last recorded Hb value during pregnancy will be mentioned.

Fibrinogen, Hb, Ht and RBCs count will be displayed in the efficacy analysis section in order to display baseline and follow-up results in the same tables.

Exploratory variables are efficacy laboratory data and will be displayed in the efficacy analysis section.

3.3.5.4 *Baseline Safety Variables*

All safety variables will be presented by study treatment group. Baseline data are defined as the last available data before the start of IMP infusion.

All laboratory data except those defined as efficacy variables (in the above section) or as exploratory variables will be defined as safety criteria. All laboratory data will not be displayed in the baseline section but in the analysis of safety in order to display in the same table the baseline and other data.

3.3.5.5 *Investigational Product (IMP) and Concomitant Treatments*

3.3.5.5.1 *Extent of Exposure*

Summary tables will display the number of patients exposed, duration of exposure (in minutes, automatically derived from the start and end times of IMP infusion), in each randomisation group and, if applicable (any error in allocation treatment), in each treatment group.

3.3.5.5.2 *Treatment Compliance*

The delay between the start of prostaglandin infusion and the start of IMP infusion (in minutes) will be presented as a continuous variable.

The same variables will be estimated and presented on the “as treated” set (SS set) in each treatment group.

3.3.5.5.3 *Concomitant Treatment*

Concomitant treatments will be coded using the WHO DDE March 1, 2014 version.

The number and percentage of patients with at least one concomitant medication will be summarised by group. Concomitant medications will be described on SS set by anatomical therapeutic chemical (ATC) name, overall and by group.

3.3.6 *Efficacy analyses*

3.3.6.1 *Primary Efficacy Variable(s) and prognostic factors*

3.3.6.1.1 *Description of the primary efficacy variable(s)*

The primary efficacy variable is a binary composite endpoint (failure versus success). Failure is defined when a patient

- loses at least 4 g/dL of Hb compared to the reference Hb level,

and/or

- requires the transfusion of at least 2 units of packed RBCs within 48 hours following the administration of IMP.

The reference Hb level is the most recent Hb value recorded during the third trimester of pregnancy.

Raw percentages of failures will be estimated within each treatment group (placebo or Clottafact®).

3.3.6.1.2 *Description of prognostic factors and covariates of the primary efficacy variable(s)*

Baseline fibrinogen will be considered as a major prognostic factor of the primary outcome. Baseline fibrinogen and centre (Centres with small number of enrolled patients (<20 patients) will be pooled arbitrary into one) will be adjusted in the primary model as described below. As the linear relationship between baseline fibrinogen and the primary binary outcome (on the logit scale) is a priori ascertained, baseline fibrinogen will be categorized into four classes (≤ 2 g/L,]2;3] g/L,]3,4] g/L, > 4 g/L).

Other possible prognostic factors will be considered secondarily and listed as follows:

- Other baseline covariates :
 - tranexamic acid intake (Yes/No),
 - lost of at least 2g/dl of haemoglobin (at V1) compared to the reference level (the last assessment during the third trimester),
 - heart rate at the inclusion (<100 beats/min vs. ≥ 100 beats/min)
 - measured/estimated total blood loss volume (<1000 ml vs. ≥ 1000 ml).

Raw percentages of failures will also be provided by centre, by tranexamic acid intake. (Yes versus No), by baseline fibrinogen (categorized into four classes: ≤ 2 g/L,]2;3] g/L,]3,4] g/L, > 4 g/L) and by other covariates levels identified above.

- Post-randomization covariates (within the 48 hours following IMP administration):
 - fibrinogen concentrate as rescue therapy,
 - tranexamic acid intake,

- administration of fresh frozen plasma,
- administration of platelet units,
- haemostatic intervention by bakri balloon,
- haemostatic invasive procedures,
- transfer to intensive care unit,
- heart rate \geq 100 beats/min.

Post-randomization covariates will be mainly used to implement the multiple imputation model for the primary analysis. Although partially confounded with the treatment effect, these post-randomization covariates will also be investigated to check whether they are treatment effect modifiers. Raw percentages of failures will be provided by post-randomization covariates levels.

